12. METHODS TO PROMOTE ADHERENCE AND MINIMIZE BIAS

12.1 Adherence

Since this study will be an inpatient study of relatively brief duration, it is not anticipated that any specific interventions will be required to promote adherence.

12.2 Blinding

This will be a double-blind, active control study. Randomization as to "high intensification" and "low intensification", as well as randomization as to continuous infusion or intermittent bolus will be double blinded.

13. PARTICIPANT SAFETY AND ADVERSE EVENTS

13.1 Institutional Review Boards

All Heart Failure Clinical Research Network sites will submit the study protocol, informed consent form, and other relevant study documents to their Institutional Review Board (IRB) for approval.

13.2 Adverse Events

13.2.1 Definitions

An **adverse event** (AE) is any sign, symptom, syndrome, or illness that occurs or worsens during the use of the test article (drug, biologic, or device) regardless of causality. A medical condition that is already present prior to treatment administration is not defined as an adverse event unless this medical condition worsens after the patient has been administered the test article. The details of these signs and symptoms will however be captured in the patient's CRF for inclusion in the database as baseline conditions. Clinically significant laboratory abnormalities (for example, abnormal ECHOs, ECGs, out of range blood parameters etc.) that occur or worsen during the use of a test article are also adverse events.

A "Serious Adverse Event" (SAE) is any adverse event that:

- Results in death
- Is life-threatening
- Requires inpatient hospitalization or prolongation of hospitalization which is not specifically required by the protocol nor is it elective.

• Results in permanent impairment of a body function or permanent damage to a body structure

• Requires medical or surgical intervention to preclude permanent impairment of a body function or permanent damage to a body structure

• Results in congenital anomaly or birth defect

Additionally, important medical events that may not result in death, be life-threatening, or require hospitalization may be considered SAEs when they jeopardize the patient or require medical or surgical intervention to prevent one of the serious outcomes listed above. Examples of such medical events include: allergic bronchospasm requiring intensive treatment in an emergency room or at home, blood dyscrasias or convulsions that do not result in in-patient hospitalization, or the development of drug dependency or drug abuse. Medical and scientific judgment must be exercised when classifying events as serious.

The relation between an adverse event and the test article will be determined by the Investigator on the basis of his or her clinical judgment and the following definitions:

Not a Reasonable Possibility- It is unlikely that the event was caused by the study drug. The temporal relationship of the adverse event to the study drug administration makes causal relationship unlikely and other drugs, therapeutic interventions or underlying conditions provide a more likely explanation for the event.

Reasonable Possibility - There is a reasonable possibility that the adverse event may have been caused by the study drug. The temporal relationship of the adverse event to study drug administration makes a causal relationship possible, and other drugs, therapeutic interventions or underlying conditions do not provide sufficient explanation for the observed event.

The intensity of the adverse event will be defined by the following criteria:

Mild :	The adverse event is noticeable to the patient but does not
	interfere with routine activity

- Moderate: The adverse event is discomforting and interferes with routine activity.
- Severe: The adverse event significantly limits the patient's ability to perform routine activities despite symptomatic therapy

An **Unexpected Adverse Event** is when the nature or severity of the event is not consistent with the applicable product information (i.e., Investigator's Drug Brochure or package insert).

The following adverse events are anticipated, disease related-events in patients with acute decompensated heart failure and therefore do not require reporting on the Adverse Event form of the CRF (although some may require reporting as study endpoints):

- Atrial fibrillation
- Ventricular tachycardia
- Myocardial infarction
- Acute coronary syndrome
- Electrolyte disturbance
- Acute renal failure
- Worsening heart failure

13.2.2 Recording and Reporting

The Site Investigator is responsible for monitoring the safety of patients enrolled into the study at the study sites. All adverse events (except those listed above) must be recorded in the Adverse Event Record of the patient's CRF and source supportive documentation must be provided to support CRF data. All adverse events should be monitored until stabilization or resolution.

Adverse events which meet the criteria of serious, study drug-related, and unexpected per the U.S. package insert, qualify for expedited reporting to the regulatory authorities. The Site Investigator will assess all SAEs occurring at his/her site and evaluate for "unexpectedness" and relationship to study drug. The Site Investigator is required to complete and submit a MedWatch Online Voluntary Reporting form (3500) for the

DOSE protocol version 18.1; February 4, 2008

events identified as serious, drug-related and unexpected at

https://www.accessdata.fda.gov/scripts/medwatch/. A copy of this report should be kept at the site and also forwarded to the Data Coordinating Center.

Investigators are also responsible for promptly reporting adverse events to their reviewing IRB/EC in accordance with local requirements.

A Data and Safety Monitoring Board (DSMB) will review safety composite data at regular intervals through-out the study.

14. STATISTICAL CONSIDERATIONS

14.1 Overview

Means, standard deviations, medians, 25th and 75th percentiles will be presented for continuous variables; the number and frequency of patients in each category will be presented for nominal variables. Statistical tests with a p value < 0.05 will be considered statistically significant, unless otherwise stated. Analyses will be performed using SAS software (SAS Institute, Inc, Cary, NC).

14.2 Analysis of Primary Endpoints

The primary analysis will be made on an intention-to-treat basis, with patients allocated to the treatment to which randomized. General linear models will be used to examine the effect of each of the main effects on the two co-primary outcomes. The dependent variables in the regression model will be the change in creatinine value from baseline to 72 hours and the AUC for the PGA VAS from baseline through 72 hours. Independent variables in the model will include the main effects of furosemide dose and mode of administration, and the baseline creatinine level. An interaction term will be included if the p-value for that parameter estimate is less than 0.025. For each co-primary outcome, the two main effects will be that the treatment (either dose or mode of administration) has no effect on either of the co-primary outcomes.

We anticipate that some patients may die before all scheduled post-baseline creatinine values can be taken, and that these losses will introduce bias into the main effects comparisons. For the primary analyses, the values imputed will be 0 for the PGA VAS after the time of death and the highest post-baseline creatinine measurement. Sensitivity analyses, including analysis of only complete cases and imputing the worst creatinine value for deaths, will be employed to assess the degree to which these missing values impact the results.

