9.1 Randomization

After providing informed consent and signing the ICF, all study subjects will be randomized using procedures determined by the DCC to one of 4 treatment groups, based on the 2 x 2 factorial design defined above. Randomization will be 1:1:1:1. Blocking will be used to ensure relatively equal distribution of patients to each arm. Randomization will be stratified by clinical site.

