9.2 Baseline Assessments

At the time of randomization, all study subjects will undergo

- Directed history and physical examination, focused on signs and symptoms of congestion
- Vital signs (including O₂ saturation and weight)
- Concomitant cardiovascular medications
- Creatinine, BUN, and electrolytes (local laboratory)
- Patient Global Well being assessment (PGA) by VAS (see Appendix C)
- Dyspnea assessment by VAS (see Appendix C)
- Blood sample for biomarkers core laboratory

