14.3 Sample Size

For purposes of power calculations, we have applied a Bonferroni adjustment to the alpha level (0.05/2 = 0.025) to allow for two co-primary endpoints. We assume that the effect of both dose and administration mode will be additive (i.e. no interaction). In our sample size calculations shown below we assess the sensitivity of the power to subadditivity of the main effects. Due to the short-term nature of the study, missing data due to loss-to-followup are expected to be rare. In addition, because this study design is testing initial treatment strategies, we do not anticipate problems with adherence to the protocol guidelines.

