14.3.2 Change in PGA VAS at 72 hours

For this measure, the maximum possible score on the VAS AUC is 7200 points (100 points x 72 hours). Based on unpublished data from the MEASURE AHF registry, the standard deviation observed for the PGA VAS AUC measure among patients with acute heart failure was approximately 1500 points (over 72 hours). With this standard deviation and the assumed 2.5% significance level, 300 patients will provide 88% power to detect a difference on the PGA VAS AUC of 600 points for each of the treatment factors.

25

Figure 6. Power to detect mean differences in general well-being VAS AUC with 300 patients at the two-sided 2.5% significance level at various standard deviations

In Table 1, we illustrate the sensitivity of the power estimates to hypothetical changes in the mean 96-hour creatinine values across the 4 treatment groups. Scenario 1 corresponds to our assumption of additivity (or no interaction) while scenarios 2 and 3 represent subadditivity and superadditivity, respectively. As expected, the power to detect main effect differences is improved if there is superadditivity of the effects and diminished if there is subadditivity of the effects.

	Low Dose & Infusion	Low Dose & Bolus	High Dose & Infusion	High Dose & Bolus	Power for the main effect tests	Power for the interaction test	Power for the 3 df overall test
Null Scenario	0.1	0.1	0.1	0.1	2.5%	2.5%	2.5%
Scenario 1 – additivity	0.1	0.3	0.3	0.5	88%	2.5%	98%
Scenario 2 – subadditivity	0.1	0.3	0.3	0.3	30%	57%	60%
Scenario 3 – superadditivity	0.1	0.3	0.3	0.7	99%	57%	99%

Table1. Sensitivity of the power to the assumption of additive treatment effects.

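### The model for the co-primary PGA VAS AUC adjusts for baseline creatinine but not for baseline PGA VAS, which gives up precision at no saving

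*Protocol*

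**What the plan says.** Protocol section 14.2 uses general linear models for the two co-primary outcomes. The dependent variables are the change in creatinine to 72 hours and "the AUC for the PGA VAS from baseline through 72 hours". One sentence then gives the covariates, without separating the outcomes: "Independent variables in the model will include the main effects of furosemide dose and mode of administration, and the baseline creatinine level". An interaction term is added only if its p-value is below 0.025. Baseline PGA VAS is not named as a covariate anywhere in the protocol.

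The value is available. Section 9.2 lists "Patient Global Well being assessment (PGA) by VAS" among the assessments at randomization, and section 11.1 and the schedule of assessments in the appendices agree. Section 9.1 stratifies randomization by clinical site only, so the design does not balance baseline PGA.

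On power for this endpoint, section 14.3.2 says that "300 patients will provide 88% power to detect a difference on the PGA VAS AUC of 600 points for each of the treatment factors", with an SD of about 1500 points taken from registry data.

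**The concern.** The covariate list fits one of the two outcomes. Baseline creatinine is the natural covariate for a change in creatinine. For the AUC, the corresponding covariate is the patient's own starting PGA score, and it is absent. Because the endpoint is the area itself and not a change from baseline, nothing else in the analysis removes differences in starting level between patients.

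Two things follow if baseline PGA predicts the AUC. The variation it explains stays in the error term, so the dose and route comparisons are less precise than the collected data allow. And a chance difference in baseline PGA between the compared groups carries over, in part, into the estimated treatment difference. Both factors are exposed, because each is tested on this endpoint.

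The covariates are not a detail left for the statistical analysis plan. The protocol states them.

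**Working it through.** **Inputs from the protocol**
- Total of 300 patients (section 14.3.2). Section 9.1 says "Randomization will be 1:1:1:1", so each main effect compares 150 with 150.
- Target difference 600 points and SD 1500 points (section 14.3.2).
- Alpha 0.025, because "we have applied a Bonferroni adjustment to the alpha level (0.05/2 = 0.025) to allow for two co-primary endpoints" (section 14.3). Figure 6 is labelled two-sided.

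**Input that is an assumption**
- The correlation ρ between baseline PGA VAS and the 72-hour AUC. The protocol gives no value. The range 0.3 to 0.6 is shown. Baseline creatinine is taken to explain none of the AUC variance. If it explains some, read ρ as the correlation that remains after adjusting for creatinine.

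**Step 1: reproduce the stated power**
- Standard error = 1500 × √(2/150) = 173.2.
- Signal = 600 / 173.2 = 3.464.
- Normal approximation: Φ(3.464 − 2.241) = 88.9%.
- Noncentral t, 296 df: 88.6%.

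Both agree with the stated 88%. The figure comes from the SD without any covariate reduction.

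**Step 2: add baseline PGA VAS**

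Residual SD = 1500 × √(1 − ρ²). The equivalent unadjusted sample size is 300 / (1 − ρ²). Power is from the noncentral t.

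| ρ (assumed) | Residual SD | Standard error | Power for 600 points | Equivalent unadjusted N |
|---|---|---|---|---|
| 0 | 1500 | 173.2 | 88.6% | 300 |
| 0.3 | 1431 | 165.2 | 91.5% | 330 |
| 0.5 | 1299 | 150.0 | 95.9% | 400 |
| 0.6 | 1200 | 138.6 | 98.1% | 469 |

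By the normal approximation, the difference detectable with 88% power is 592 points at ρ = 0, 564 at 0.3, 512 at 0.5 and 473 at 0.6.

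**Step 3: chance imbalance without the covariate**

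The baseline difference between groups has standard error SD_b × √(2/150), where SD_b is the SD of baseline PGA. The AUC moves by ρ × 1500 / SD_b points per baseline point. SD_b cancels, so the 95% range of the shift in the AUC difference is ±1.96 × ρ × 1500 × √(2/150):
- ρ = 0.3: ±102 points (17% of the 600-point target)
- ρ = 0.5: ±170 points (28%)
- ρ = 0.6: ±204 points (34%)

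**Step 4: is the assumed range plausible?**

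Readings at 0, 6, 12, 24, 48 and 72 hours enter the area. By the trapezoid rule the baseline reading has a weight of 3 of 72 hours (4.2%), so its direct contribution is small. Any useful correlation must come from persistence within the patient. If all six readings were equally correlated at 0.3 (an assumption), the correlation of baseline with the AUC would be 0.49, inside the range shown.

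**The case against.** The best defence is that nothing here is invalid. Patients are randomized, so leaving out a prognostic baseline causes no bias on average and does not inflate the type I error. Chance imbalance in baseline PGA is already part of the sampling variation that the unadjusted standard error covers. The sample size was set on the unadjusted SD, so the trial has its planned power without the covariate. All of this stands. The gain is extra power, and no shortfall is being repaired.

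A reader might infer more than the protocol supports, in three ways.
- That baseline creatinine has no place in the AUC model. Section 4.4 says that renal function may influence diuretic response, and section 14.5 plans to test baseline creatinine as an effect modifier. That is a modest reason to keep it, though it does not show that creatinine can stand in for baseline PGA.
- That baseline PGA is known to be the strongest predictor of the AUC. This is the usual expectation for an outcome's own baseline, but the protocol reports no correlation.
- That each point of baseline imbalance adds 72 AUC points. This would require the difference to persist undiminished for 72 hours. If baseline PGA had an SD of about 1500/72 = 20.8 points (an assumption), the shift would be 72 × ρ, or about 22, 36 and 43 points at ρ = 0.3, 0.5 and 0.6.

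It can also be said that the wording does not exclude further covariates. That is only a partial answer. The one list applies to both outcomes as written, and a covariate that is added later without having been named invites the question of whether the imbalance had been seen first.

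The point does not extend to the secondary dyspnea VAS AUC. Section 14.4 fixes no covariate list for it, so there is nothing there to correct.

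**Conclusion.** The point holds as a matter of efficiency. As written, the PGA VAS AUC is adjusted for the other co-primary outcome's baseline and not for its own. At an assumed correlation of 0.3 the gain is small, about 3 percentage points of power. At 0.5 to 0.6 it is 7 to 9 points, equivalent to 100 to 169 more patients in an unadjusted analysis. The direction is secure if baseline PGA has any appreciable correlation with the AUC. The size depends wholly on a correlation that the protocol does not give. The change is worth making before unblinding because it is nearly free, and because efficacy on both factors rests on this endpoint.

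**What to change.** In protocol section 14.2, replace the shared covariate sentence with one list per outcome:
- Creatinine change: dose, mode of administration and baseline creatinine, as now.
- PGA VAS AUC: dose, mode of administration and baseline PGA VAS, with baseline creatinine either kept or dropped. State which.

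Replacing creatinine in the AUC model costs no further degree of freedom, and adding PGA to it costs one. No new data, visits or patients are needed, and the power statement in section 14.3.2 can stay as it is, as a conservative figure.

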6. STUDY POPULATION AND ELIGIBILITY CRITERIA

6.1 Inclusion Criteria

- Male or female patient \geq 18 years old
- Prior clinical diagnosis of heart failure with daily home use of oral loop diuretic for at least one month
- Daily oral dose of furosemide \geq 80 mg and \leq 240 mg (or equivalent)
- Must be identified within 24 hours of hospital admission
- A diagnosis of heart failure as defined by the presence of at least 1 symptom (dyspnea, orthopnea, or edema) AND 1 sign (rales on auscultation, peripheral edema, ascites, pulmonary vascular congestion on chest radiography)
- Anticipated need for IV loop diuretics for at least 48 hours
- Willingness to provide informed consent

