7.1 Randomization to 48 hours

Patients will be randomized in a 1:1:1:1 ratio to one of the 4 treatment combinations (2x2 factorial design).

- Low intensification strategy for IV furosemide (1 x outpatient oral dose) by continuous infusion
- Low intensification strategy for IV furosemide (1 x outpatient oral dose) by intermittent bolus Q12 hours
- High intensification strategy IV furosemide (2.5 x outpatient oral dose) by continuous infusion
- High intensification strategy (2.5 x outpatient oral dose) by intermittent bolus Q12 hours

If the outpatient dose has changed over the week prior to admission, the outpatient dose will be defined as that received 7 days prior to randomization for the sake of this study.

For patients receiving outpatient loop diuretics other than furosemide, conversion to furosemide equivalents will be as follows:

1 mg torsemide = 2 mg furosemide

1 mg bumetanide = 40 mg furosemide

If patients are deemed to have had an adequate response to diuretics prior to 48 hours, they will be permitted to change to oral diuretic therapy (open label dosing at investigators' discretion.)

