14.3.1 Change in Creatinine at 72 hours

The standard deviation observed for the change in creatinine from baseline to discharge in the ESCAPE trial (unpublished data) was 0.47 mg/dL. Similarly, in the control arm of the UNLOAD study (unpublished data), the standard deviation of the change in creatinine from baseline to discharge was 0.5 mg/dL. With 300 patients, we will have approximately 88% power to detect a difference in mean creatinine of 0.20 mg/dL for each main comparison, assuming a standard deviation of 0.5 mg/dL. Assuming a smaller standard deviation of 0.4 mg/dL, we would have approximately 98% power to detect a difference of 0.2 mg/dL. The effect of various standard deviations on the power to detect given mean differences in peak creatinine (mg/dL) at the 2.5% significance level is given in Figure 5.

Figure 5. Power with 150 patients per group to detect various mean differences in creatinine (mg/dL) assuming normal distribution with various standard deviations at the two-sided 2.5% significance level

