14.5 Subgroup Analyses

Further analyses will be conducted to determine whether the effect of furosemide dose or mode of administration is modified by each of the following covariates:

- Admission blood pressure
- Baseline creatinine ($\leq 1.6 \text{ v.} > 1.6 \text{ mg/dL}$)
- Age (≤ 70 v. > 70)

Estimation of subgroup effects will be conducted within the linear models framework. To provide a conservative framework for the interaction testing, we will consider the interaction terms to be statistically significant if p<0.001.

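### Home loop-diuretic dose sets every patient's starting study dose, yet it is neither a covariate in the primary models nor a listed effect modifier; adding it is a small, nearly free improvement

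*Protocol*

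**What the plan says.** - **Eligibility (Protocol 6.1).** The criterion headed "Daily oral dose of furosemide" admits 80 to 240 mg/day, or the equivalent in another loop diuretic.
- **Treatment (Protocol 5 and 7.1).** Study dose is a multiple of that home dose: 1 x in the low strategy and 2.5 x in the high strategy, for example "High intensification strategy IV furosemide (2.5 x outpatient oral dose) by continuous infusion". Section 7.1 also says which home dose counts if it changed in the week before admission, and how to convert torsemide and bumetanide.
- **Randomization (Protocol 9.1).** Stratified by clinical site only.
- **Primary models (Protocol 14.2).** For both co-primary outcomes: "Independent variables in the model will include the main effects of furosemide dose and mode of administration, and the baseline creatinine level".
- **Effect modifiers (Protocol 14.5).** The plan asks whether either treatment effect is "modified by each of the following covariates", and lists admission blood pressure, baseline creatinine and age. An interaction counts as significant only at p<0.001.
- **Power (Protocol 14.3 and 14.3.1).** On alpha: "we have applied a Bonferroni adjustment to the alpha level (0.05/2 = 0.025) to allow for two co-primary endpoints". For creatinine: "approximately 88% power to detect a difference in mean creatinine of 0.20 mg/dL for each main comparison, assuming a standard deviation of 0.5 mg/dL".

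**The concern.** Home dose is a baseline value that the design builds into the treatment. Two patients in the same arm can start on doses that differ threefold, and the mg gap between strategies also differs threefold across the eligible range. Section 11.1 justifies creatinine as the safety endpoint by the observed link between diuretic dosage and worsening renal function. If that link holds in mg, home dose predicts creatinine change within each arm and also scales the high-versus-low effect.

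Two things would then be at stake. A little precision is given up by leaving out a covariate that is already available. And one average effect could describe neither an 80 mg patient nor a 240 mg patient well, while the modifier analyses the protocol lists would not examine this.

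**Working it through.** **1. The plan's own power.** Inputs: 150 per group and a two-sided 2.5% level (14.3.1, Figure 5 caption), difference 0.20 mg/dL, SD 0.5 mg/dL.

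- Standard error = 0.5 x sqrt(2/150) = 0.0577.
- Power = Phi(0.20/0.0577 - 2.241) = Phi(3.464 - 2.241) = 88.9%. The noncentral t gives 88.6%. Stated: 88%.
- At SD 0.4: 98.2%. Stated: 98%.
- For the global well-being AUC, 600/1500 is the same standardized difference, so power is again 88.9%. Stated: 88%.

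The stated figures reproduce.

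**2. The contrast by home dose.** Gap = (2.5 - 1) x home dose.

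| Home dose (mg) | Low (mg) | High (mg) | Gap (mg) | Ratio |
|---|---|---|---|---|
| 80 | 80 | 200 | 120 | 2.5 |
| 160 | 160 | 400 | 240 | 2.5 |
| 240 | 240 | 600 | 360 | 2.5 |

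The mg gap varies threefold; the ratio does not vary.

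**3. Precision forgone for creatinine, if the response is linear in mg.** Assumptions, not in the documents: mean home dose m of 130 to 150 mg, SD s of 31 to 52 mg, and an average effect of 0.20 mg/dL.

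- Slope per mg: b = 0.20/(1.5 x m).
- The outcome slope on home dose is b in the low arm and 2.5b in the high arm. A single covariate fits the average, 1.75b.
- R-squared of that covariate = (1.75 x b x s)^2 / 0.25.
- Separate slopes in each arm would explain (1 + 6.25)/2 = 3.625 x (b x s)^2 / 0.25. The single covariate recovers 1.75^2/3.625 = 84% of that.
- Power = Phi(3.464/sqrt(1 - R-squared) - 2.241).

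| m, s (mg) | b x s | R-squared | Power |
|---|---|---|---|
| no covariate | - | 0 | 88.9% |
| 150, 31 | 0.0276 | 0.9% | 89.2% |
| 130, 31 | 0.0318 | 1.2% | 89.3% |
| 150, 52 | 0.0462 | 2.6% | 89.8% |
| 130, 52 | 0.0533 | 3.5% | 90.1% |

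The gain is about 0.3 to 1.1 percentage points (difference of unrounded powers).

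**4. Effect modification under the same assumption.**

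- Effect at 80 mg: 0.20 x 80/m = 0.11 to 0.12 mg/dL. At 240 mg: 0.32 to 0.37 mg/dL.
- Change in effect per SD of home dose: 1.5 x b x s = 0.04 to 0.08 mg/dL.
- Standard error of that slope: 2 x 0.5/sqrt(300) = 0.058, so z is about 0.7 to 1.4.
- The 14.5 threshold of p<0.001 needs |z| above 3.29. Power is Phi(0.72 - 3.29) to Phi(1.39 - 3.29), about 0.5% to 3%.

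**5. The other scale.** If creatinine change is linear in log dose with slope c, high minus low is c x [ln(2.5h) - ln(h)] = c x ln 2.5 at every home dose h. Home dose would still predict outcome within each arm, but the strategy effect would be constant.

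**The case against.** **The trial compares strategies.** Sections 7.5 and 14.3 describe initial strategies, so an average effect of the multiplier is the intended quantity, and on the relative scale the contrast is 2.5-fold for everyone. This stands. It is why the mg gap alone does not show that the effect differs by home dose. The proposed covariate leaves the strategy contrast as it is.

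**Outcome variation due to home dose is not documented.** This also stands. Section 4.1 concerns mortality, and says dosing is not closely linked to other measures of severity. Section 4.2 concerns doses in observational data that it calls heavily confounded. Section 4.3 reports no association between diuretic dose and relief of dyspnea, which gives no encouragement for the well-being AUC. Baseline creatinine is already in the model and may carry part of whatever home dose would add. Early oral switch, the 50% increase at 48 hours and open-label rescue all loosen the tie between home dose and exposure over 72 hours.

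**An analysis plan could add the covariate.** It could, since the wording of 14.2 is not strictly exhaustive. But the protocol does name the covariate and the three modifiers, so naming home dose in advance avoids a later choice made after the data are seen.

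**Stronger readings.** A reader might infer that leaving out home dose biases the dose comparison, or that the sample size is wrong. Neither follows. Randomization makes home dose independent of assignment, and the power figures rest on SDs not adjusted for home dose and reproduce. With an effect proportional to mg (0.10 mg/dL at 80 mg, 0.30 at 240 mg), the heterogeneity raises the residual SD from 0.500 to at most 0.505, and power stays at 88.3 to 88.8%.

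**Conclusion.** The point holds as a minor improvement. Home dose determines the starting study dose, varies the mg contrast from 120 to 360 mg, and is in neither list. The randomized comparison is unbiased without it, and no stated figure is invalidated.

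For creatinine, the gain is about 0.3 to 1.1 points of power, assuming a response linear in mg, an average effect of 0.20 mg/dL, and a mean home dose of 130 to 150 mg with SD 31 to 52 mg. It could be smaller once baseline creatinine is accounted for. For the well-being AUC no gain has been shown; the covariate there would be for consistency.

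A reader might also infer that the treatment effect is known to be three times larger at 240 mg than at 80 mg. The documents support only a threefold gap in mg. Whether the effect follows depends on the dose-response scale, which they do not settle. The trial cannot test this usefully at p<0.001, so the value of looking is descriptive.

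**What to change.** - **14.2:** prespecify baseline home furosemide-equivalent dose, defined and converted as in 7.1, as a continuous covariate alongside baseline creatinine in both co-primary models.
- **14.5:** add it as a continuous modifier of the dose-strategy effect. Report the estimated high-minus-low difference with its confidence interval across 80 to 240 mg, labelled as estimation only and outside the p<0.001 rule.
- **Scale:** state in advance whether home dose enters in mg or on the log scale, and what each implies: modification is expected if the response is linear in mg, and none if it is linear in log dose.

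The cost is one degree of freedom in each primary model and one more estimate in the subgroup report. The value is already needed to establish eligibility and prepare study drug, so no new data, patients or change to treatment are required.
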